- 1) Tetrahydrocannabinol (THC) has been the primary focus of cannabis research since its isolation and synthesis in 1964 (Gaoni and Mechoulam 1964). Currently there is a lot of debate regarding whether, and which, non-THC constituents of the cannabis plant contribute to the overall pharmacodynamic effects of cannabis. In recent publications, Ethan Russo has hypothesized that specific cannabis terpenoids, aromatic essential oil (EO) components, may selectively mitigate or exacerbate some acute effects of THC (McPartland and Russo 2001, Russo 2011, McPartland and Russo 2014). This purported "entourage effect" has been the driving force behind state legalization of cannabis for medicinal purposes despite THC (as dronabinol) being available as an FDA approved medication. However, there have been no empirical research studies conducted to evaluate the interactions of THC and terpenoids found in the cannabis plant. The proposed study will be a controlled human laboratory evaluation of the acute dose effects of THC and alpha-pinene (pinene) alone and in combination. Pinene is a flavor and fragrance component common to many plants (e.g., conifers), is one of the most abundant terpenoids in cannabis, is a fragrance ingredient in many household products, and is part of the typical human diet as it is a common food additive found in baked goods, beverages, candy, and ice cream. Oral ingestion of pinene is Generally Recognized as Safe (GRAS) by the US Food and Drug Administration and other regulatory agencies, and studies have been conducted evaluating its effects when inhaled in ambient air. Prior pre-clinical research has demonstrated that pinene administration can enhance memory (Buchbauer et al. 1993, Carvalho-Freitas and Costa 2002, Pultrini Ade, Galindo, and Costa 2006, Falk-Filipsson et al. 1993). Further evidence for pinene's potential as a memory enhancer, is the fact that it shares the same mechanism of pharmacological action (i.e., acetylcholinesterase inhibitor) as many medications prescribed to combat dementia (Perry et al., 2000). This study will evaluate whether pinene, compared with placebo, attenuates the memory impairing effects that often occur following acute THC administration. A controlled laboratory study will be

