The aim of the proposed study is to evaluate, in a controlled laboratory experiment, whether and to what degree, pinene modulates the acute effects of inhaled THC. The procedures being used have been established in our lab during recent studies evaluating the dose effects of cannabis administered via oral ingestion, smoke, or vaporization. Results of those studies demonstrate that we can reliably produce and validly measure acute cannabis effects and were used to inform the THC doses selected for this study. We safely administered vaporized cannabis containing THC doses up to 25mg to healthy adult volunteers in a recent study (IRB00035394) without occurrence of unanticipated or serious adverse events. These doses produced dose-orderly drug effects. The 25mg THC produced moderate to high memory impairment as assessed using a working memory task (the Paced Serial Addition Task; PASAT) in these participants (see Figure below). In pilot testing of this protocol in 3 participants, however, we found that the 25mg doses of pure THC did not produce impairment of cognitive functioning. However, data from a concurrently run protocol (IRB00085652) vaporization of 30mg of THC reliably produced memory performance impairment, but was well tolerated by study volunteers. Thus, we have selected the THC dose of 30mg in order to test the ability of pinene to attenuate mild and moderate impairment of cognitive functioning induced by acute THC administration. Therefore, the study will address the cognitive and psychomotor impairment of placebo, pinene alone, and 30mg THC alone or combined with 0.5, 5, and 15mg of pinene.

The doses of pinene to be used in this study (0.5mg 5mg, and 15mg) were chosen based on comprehensive analyses performed on 107 samples of cannabis, representing 29 unique cannabis "strains", being sold by a licensed medical cannabis producer, Tilray, in Canada. Specifically, these analyses revealed that the mean (range) concentration of pinene in the cannabis samples was 0.05% (0 – 0.5%), meaning 1 gram of cannabis would, on average,

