contain 0.5mg of pinene and as high as 5mg of pinene. Importantly, 1 gram is the amount of plant material commonly used to make a single cannabis cigarette ("joint" or "blunt"). Thus, these doses are ecologically relevant and have demonstrated safety with respect to acute dosing via direct inhalation. The additional 15mg dose of pinene is higher than what would typically be consumed in 1 g of natural cannabis, but reflects the current practice in the cannabis industry in which terpenes are extracted from cannabis separately from cannabinoids and then reconstituted at unnatural ratios. The addition of the 15mg pinene dose is an amendment to the original protocol, at which time no adverse effects had been reported following either 0.5mg or 5mg pinene doses for the first 13 randomized participants and exposure to both doses of pinene did not differ from placebo on any pharmacodynamic outcomes assessed.

The results of this study will represent a significant initial advancement in understanding the behavioral pharmacology of cannabis. This is the second study in a series of similar experiments funded by NIH in which we will begin to systematically evaluate the interactions of multiple components of the cannabis plant. The first study (IRB00085652) showed that the terpene limonene exhibited a dose-orderly reduction in the acute anxiogenic effects of high doses of THC. In that study, as in this one, small effects were observed at low and medium doses (1mg and 5mg limonene), but 15mg limonene significantly reduced anxiety, paranoia and similar subjective effects compared with 30mg THC in the absence of limonene. Notably, the 15mg limonene dose also exceeded the amount typically found in a 1g cigarette of natural cannabis, so there is precedent from this prior study in needing to increase the maximum dose of terpenes in order to observe robust effects on target endpoints. Characterization of the interaction between THC and pinene will provide an initial scientific basis for whether or not there is benefit for including terpenoids in the development of cannabinoid-based pharmaceutical products as one means of reducing the incidence and/or severity of side effects.

4. Study Procedures

a. Study design, including the sequence and timing of study procedures (distinguish research procedures from those that are part of routine care).

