- 3) Cognitive performance tests at 0, 30 min, 60 min, 90 min, 120 min, 180 min, 240 min, 300 min, and 360 min (Episodic memory tests will only be administered at 30 min and 360 min).

Use of medication or tobacco products will not be allowed during the study sessions. Study participants who regularly use tobacco products will be provided a nicotine patch upon request.

Outpatient Discharge. Participants will be discharged after completing final assessments (approximately 6 hours post-exposure). In prior studies conducted in our laboratory, this timeline has been adequate for healthy adults to resolve any effects from acute doses of cannabis that are similar to those used in the present protocol. If a study participant indicates the desire to be discharged from the study early, BPRU medical staff will review the self-reported rating of "drug

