The selection of doses was conducted to balance the study aim, participant safety and tolerability based on previous experience, and ensuring that doses are ecologically valid. In our laboratory, tolerant daily cannabis users have safely self-administered up to 3 grams of smoked cannabis containing 10% THC (300mg THC) within one hour (protocol NA 00082269). More recently, acute oral, smoked and vaporized administration of 5mg to 30mg THC to infrequent cannabis users (as will be recruited here) resulted in dose-dependent drug effects (IRB00035394, IRB00122849, IRB00085652). At doses of 10-15mg THC, participants reported an increase in pleasant drug effects with few unpleasant side effects and mild impairment of working memory was observed for a subset of participants. At 25-30mg THC doses, there was ratings of pleasant drug effects were comparable to the 10-15mg doses, but working memory performance was significantly impaired; there were also no unanticipated or serious adverse events in this dosing condition. Moreover, inspection of the individual-level data showed that 14/17 study completers exhibited a decrease in performance of 10 or more correct responses compared with baseline on the PASAT following administration of the 25 mg THC vaporized whole plant cannabis and the mean reduction in PASAT scores after 30mg pure THC was also about 10 correct responses (this magnitude of change signifies moderate impairment of working memory). Thus, based on prior studies and pilot testing of this protocol, we believe that a 30 mg THC dose will be sufficient to produce moderate to high memory impairment in most participants in the present study, thus allowing us to examine our proposed hypothesis, but this dose should still be well tolerated by study participants without putting them at risk of significant discomfort or danger.

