THC is FDA approved as an oral formulation (dronabinol; Marinol). Pinene is Generally Recognized as Safe (GRAS) for oral consumption. Neither THC or pinene is FDA approved via the pulmonary route. As detailed above, we believe that the THC and pinene administration in this study will be safe for cannabis-experienced participants. The route of administration (vaporization) is common for cannabis self-administration and the doses of both THC and pinene are within the range of what would be expected in real-world cannabis use scenarios. We have submitted an IND application to the FDA for the conduct of this experiment.

c. Justification and safety information if non-FDA approved drugs without an IND will be administered.

N/A

Study Statistics

a. Primary outcome variable.

The primary outcome measure for this study is the total correct on the PASAT (test of working memory).

b. Secondary outcome variables.

Secondary outcome measures include total correct on the International Shopping List Test (test of episodic memory), Reaction Time for Correct Trials on the PASAT, Number Correct on the DSST, self-reported rating of "Trouble With Memory" on the DEQ, and composite score of the Confusion-Bewilderment sub-scale of the POMS.

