The sample size estimate for this study was based on previous work in this laboratory evaluating dose effects of acute drug administration using a within-subjects design. A meta-analysis was previously conducted comparing the statistical power of 13 drug effect assessments from six dose-effect studies, with 14 participants each, evaluating a range of abused drugs in our laboratory (Felch, Di Marino, and Griffiths 1996). The analysis showed that average effect size for primary measures (i.e. subjective drug effect ratings, staff ratings and behavioral/cognitive performance measures) ranged from approximately 0.87 to 1.0. Based on this estimate of effect size, the proposed sample size of 20 should be adequate to assess the expected effects and to differentiate low from high doses. This sample selection methodology has been consistent in our long history of studies investigating acute dose-effect comparisons of cannabis/THC. These methods have excellent external validity and have become the FDA recommended standard for human abuse liability assessment. Subjective drug effect and mood ratings, vital signs and cognitive performance outcomes will be assessed using multiple regression analyses appropriate for repeated measures testing based on the final characteristics of the data set (e.g. normal distribution, skewness, kurtosis).

c. Early stopping rules.

The study will be stopped if new information is learned that indicates a serious risk to study participants.

7. Risks

a. Medical risks, listing all procedures, their major and minor risks and expected frequency.

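### Participants who return for the 15 mg pinene sessions always take them after THC alone, and the PASAT analysis names no adjustment for session order or return visits

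*Combined protocol and SAP*

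**What the plan says.** Under Study Statistics, item a: "The primary outcome measure for this study is the total correct on the PASAT (test of working memory"). The score is the number correct out of 90 in one administration (Study Measures). The post-drug schedule lists "Cognitive performance tests at 0, 30 min, 60 min, 90 min, 120 min, 180 min, 240 min, 300 min, and 360 min", and the Baseline Assessments paragraph adds a pre-dose battery that includes working memory.

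The Background says the study will cover "placebo, pinene alone, and 30mg THC alone or combined with 0.5, 5, and 15mg of pinene". The opening summary asks whether pinene "attenuates the memory impairing effects that often occur following acute THC administration", so the contrast of interest is THC plus pinene against THC alone, at three pinene doses.

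The only analysis text closes the sample-size paragraph of Study Statistics. Pharmacodynamic outcomes will be assessed with "multiple regression analyses appropriate for repeated measures testing based on the final characteristics of the data set (e.g. normal distribution, skewness, kurtosis").

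On order, the Protocol Overview randomises the sessions. The Participants paragraph makes an exception: those who finished before 15 mg pinene was added are invited back for the two new conditions only. The placebo justification in section 4 lists learning effects among the things that placebo is meant to control.

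**The concern.** In a crossover, random order spreads practice, fatigue and calendar effects evenly over conditions. That fails for returners. Their THC-alone session belongs to the first round and their THC plus 15 mg session to the return round, without exception. Their placebo session also belongs to the first round, so it says nothing about performance on return.

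Anything that shifts PASAT scores between the two rounds therefore goes into the 15 mg versus THC-alone contrast. A practice gain raises the later scores and looks like pinene protecting working memory. A decline would do the opposite. This is the dose that the Background adds in the hope of seeing clearer effects, so the conclusion most likely to be drawn from the trial is the one exposed.

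A lesser issue concerns the three dose contrasts. No alpha, deciding dose or multiplicity rule is stated, so a significant result at any one dose could be reported as the primary finding.

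**Working it through.** **The plan's own figure.** The plan calls 20 completers adequate for an effect size of 0.87 to 1.0, without stating alpha, sidedness or power. Read as one paired comparison at two-sided 0.05, n = 20 gives power of 95.8% at 0.87 and 98.9% at 1.0. The sample size is not the problem here.

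**Inputs.** From the documents: 20 completers, 40 randomised to obtain them, 13 randomised when the 15 mg text was written, three THC plus pinene doses, and a THC effect on the PASAT described thus: "the mean reduction in PASAT scores after 30mg pure THC was also about 10 correct responses". Assumed: half of the 13 complete and all of those return, 13 × 20/40 = 6.5, so k = 6 to 7; four or six conditions in the first round (the documents do not say); two-sided 0.05.

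**Session lag.**
- Four earlier conditions: the return sessions are numbers 5 and 6 (mean 5.5), and THC alone averages 2.5. The lag is 3 sessions per returner.
- Six earlier conditions: return sessions 7 and 8 (mean 7.5) against 3.5. The lag is 4.
- Participants randomised to all six current conditions: expected lag 0.
- Mean over 20: 3k/20 = 0.90 (k = 6) or 1.05 (k = 7); 4k/20 = 1.20 or 1.40.

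The expected lag is thus 0.9 to 1.4 sessions; actual random orders scatter around it. Bias equals lag times gain per session. The documents give no gain. As an illustration, 0.5, 1 and 2 correct per session give 0.45 to 0.7, 0.9 to 1.4 and 1.8 to 2.8 correct in pinene's favour, against a THC effect of about 10.

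**A one-off return-visit shift.** Unadjusted, the share entering the contrast is k/20 = 0.30 to 0.35. Least-squares fits with participant effects over many random orders give:
- Linear session term: 0.24 to 0.29 remains, although a steady per-session gain is removed.
- Categorical session: 0.24 to 0.27 remains with four earlier conditions, because returners share session numbers 5 and 6 with everyone else. About 0 remains with six.
- Return-visit indicator: 0, because conditions are then compared only within a round.

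If practice levels off by session 3, a linear term over-corrects: -0.13 to -0.28 per point of gain, against +0.15 to +0.25 with no term.

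**Precision cost for THC plus 15 mg versus THC alone.**
- Linear session: 2 to 3% wider standard error. Categorical: 5% (four earlier conditions) or 11 to 13% (six).
- Return-visit indicator, four earlier conditions, unit residual variance. Split the contrast into three orthogonal parts: half the difference between the two 15 mg conditions (variance 0.5 per person), the mean of those two minus the mean of the other four (0.75), and the mean of those four minus THC alone (0.75). Only the middle part loses the returners. Variance = 0.5/20 + 0.75/(20 - k) + 0.75/20, against 2/20 = 0.100. For k = 6 this is 0.1161, ratio √1.161 = 1.08. For k = 7 it is 0.1202, ratio √1.202 = 1.10.
- Only those randomised to all six conditions together (14 or 13 people): √(20/14) = 1.20 or √(20/13) = 1.24.

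**Three dose contrasts.** Simulation with n = 20, no pinene effect, one PASAT summary and an assumed paired THC effect of 0.5 to 1.0 gives a 12 to 13% chance of at least one significant contrast with THC alone, and 6 to 7% favouring pinene. One test gives 5% and 2.5%. Requiring a significant six-condition omnibus first leaves this at 12 to 13%, because THC itself makes the omnibus significant 79 to 100% of the time.

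**The case against.** The strongest reply is that the practice effect may be negligible. Participants train to a stable level at screening, and the example entry criterion of 75 out of 90 leaves limited headroom. The number of returners is unstated, and so is any gain. That stands: the direction of the bias is known, its size is not. It does not remove the need to model order, since the plan itself treats learning as something to control.

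A second reply is that the stated objective is to examine effects, so an unspecified dose hierarchy is partly a matter of convention. That also stands, which is why multiplicity is secondary here.

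Three stronger readings are tempting and are not supported:
- That the primary contrast was examined before 15 mg was added. The Background says "exposure to both doses of pinene did not differ from placebo on any pharmacodynamic outcomes assessed". Since THC impairs performance, this most naturally means pinene without THC. It also says "In that study, as in this one, small effects were observed at low and medium doses", which hints at combination data but names no outcome. The documents already disclose both statements.
- That the model will be chosen on treatment results. The examples given are distributional features only.
- That any time summary could be picked. A repeated-measures regression naturally uses all nine times. The plan leaves the time handling unstated, but an error rate for choosing among summaries would rest on summaries that the plan never mentions.

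**Conclusion.** The concern holds for returners. Dose and testing round are confounded in the THC plus 15 mg versus THC-alone contrast, and the analysis text contains nothing to separate them. With 6 to 7 returners the expected lag is 0.9 to 1.4 sessions, and 30 to 35% of any return-visit shift passes into the contrast. This rests on the assumed number of returners and of earlier conditions.

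A reader might infer that the 15 mg result will be biased towards pinene by a known amount, or that a linear session term would cure the problem. Neither follows: no gain per session is documented, and a linear term leaves most of a return-visit shift in place.

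The secondary point also holds: about a 13% chance of some false-positive dose contrast, 6 to 7% favouring pinene, at an assumed two-sided 0.05 with no adjustment. These are gaps in the analysis plan that the design can still accommodate.

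**What to change.** Before final unblinding, add the following to Study Statistics.

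1. Primary PASAT model: condition, session number and that session's pre-dose PASAT as fixed effects, with a random participant effect.
2. A return-visit indicator. Categorical session can replace it only if returners' session numbers are not shared with other participants.
3. The 15 mg versus THC-alone estimate and confidence interval, reported also in participants randomised to all six conditions together. State in advance what counts as a material difference; if there is one, base the 15 mg conclusion on that set.
4. One way of handling the nine PASAT times for the primary contrast, with single-time contrasts descriptive.
5. One multiplicity rule for the three dose contrasts, Holm or a fixed order, at the sponsor's choice.

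**Cost.** No new data are needed. The 15 mg standard error widens by 2 to 3% for a linear session term, 5 to 13% for a categorical one and about 8 to 10% for the indicator. The all-six set is only 13 to 14 people, with a standard error 20 to 24% larger. How much the pre-dose PASAT would recover is unknown.

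The multiplicity rule costs power for individual doses. Read the plan's 0.87 to 1.0 as THC's paired effect and suppose that one dose reverses half of it. After a THC-versus-placebo gate, a fixed order starting at 15 mg keeps 45 to 57% power for 15 mg, as without adjustment, but finds an effect confined to 5 mg only 2% of the time. Holm gives 28 to 37% in either case.
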